1. STUDY OBJECTIVES

1.1 Primary Objectives

- I. Identify SMT protocol components and interactions that independently predict SMT mechanistic outcomes (spinal stiffness and multifidus activation). We hypothesize that one or more combination of components will be identified that optimize improvement in SMT mechanisms.
- II. Identify SMT protocol components and interactions that independently predict SMT patient-centered outcomes (function, pain). We hypothesize that one or more combination of components will be identified that optimize improvement in patient-centered outcomes.

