9.2 Sample Size and Randomization

Based on our past trials, we project 95% retention at 4-weeks. We estimated standard deviations of each outcome based on patients in a similar project with analogous eligibility criteria, and conservatively estimated pre-post correlations to be 4%-7% smaller than the values in this study. Assuming a sample size of 316, of which 280 meet all eligibility criteria and 92% of enrolled participants are retained to 4 weeks, the table below displays minimum detectable effect sizes for a) main effects of each protocol component, b) pairwise interactions between components, c) comparison of mean outcome between two levels of one component at a fixed level of another component, d) main effects of the 3 components in subgroup analyses involving half the participants, and e) pairwise interactions between 2 components in subgroup analyses with half the participants. This sample size provides at least 80% power to detect the MCID or hypothesized effect sizes for the main effects of each component for all outcomes, and for analyses of main effects in subgroups and conditional comparisons for each outcome except global stiffness. Power is more limited for secondary aims, such as pairwise interactions within subgroups.

	Assumptions for Outcome Measures in Project			
	Global Stiffness (N)	Multifidus Activation (mm)	Oswestry	Numeric Pain Rating
Assumption				
Mean (SD)	5.55 (1.60)	2.60 (0.124)	24.3 (14.9)	5.06 (2.12)
Pre-post score correlation	0.80	0.70	0.70	0.45
MCID or hypothesized effect size from past work	0.40	0.074	6.0	2.0
Type of effect	Detectable Effect Size			
Main effect	0.37	0.034	4.12	0.76
Pairwise interaction	0.74	0.064	8.24	1.53
Conditional comparison	0.53	0.045	5.83	1.08
Main effect in 50% of subjects	0.53	0.045	5.83	1.08
Interaction in 50% of subjects	1.05	0.091	11.65	2.16

Table. Assumptions and detectable effect sizes informing sample size for the project.

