9.6 Data Analyses

Primary Aim 1: Spine stiffness and multifidus activation will be co-primary outcomes for evaluating effects of SMT protocol components on SMT mechanisms. The effect of intervention components (A additional SMT; B multifidus activation; C mobilizing exercises) on each outcome will be evaluated using linear mixed models to relate mean levels of each outcome at 1-, 4-weeks and 3-months to indicator variables to represent the main effects of each interventions (A, B, C) as well as each pairwise interaction between the interventions (AxB, AxC, BxC) and the 3-way interaction (AxBxC). 1-week assessment, which occurs just before randomization, will serve as the baseline for these analyses and the model will be assumed equal between the randomized groups. This model, sometimes referred to as a constrained longitudinal model, leads to adjustment for baseline levels as in analysis of covariance (ANCOVA), which has been shown to remove conditional bias in treatment group comparisons due to chance imbalances and improve statistical power over unadjusted comparisons. An unstructured covariance matrix will be used to account for correlation of serially measured outcome scores in the same subject. By using an unstructured covariance matrix, the model will constitute a special case of a general linear mixed model which avoids imposing specific assumptions concerning distribution of random effects. This modelling approach is recommended in randomized trials when the number of follow-up outcome assessments is small. Restricted maximum likelihood estimation will be used for estimation of parameters and their associated standard errors.

Linear mixed effects analysis will provide estimates and CIs for the following quantities for each outcome at both 4-week and 3-month assessments: a) Main effects evaluating effects of each of the 3 interventions while averaging over the levels of the other 2 interventions. b) Three pairwise interactions evaluating if the effect of an intervention differs between levels of another interventions, while averaging over levels of the 3rd intervention. Pairwise interactions will inform whether the effects of each intervention pair are additive, synergistic or antagonistic. c) 3-way interaction evaluating if each pairwise interaction differs depending on the 3rd intervention.

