Adjusted means with CIs will be provided for each treatment combination. Interaction plots will be used to depict significant interactions and linear contrasts constructed to evaluate the effect of each intervention conditional on the presence or absence of the other intervention. To account for 2 primary outcomes, each of the hypothesis tests noted above will be performed with 2-sided $\alpha=0.025$ and confidence intervals will be constructed using a confidence coefficient of 0.975. The indicated comparisons at 4-weeks will be given primary emphasis in evaluating the effects of each intervention. Comparisons at 3-months will evaluate persistence of effects following intervention.

Primary Aim #2: The OSW and NPRS will be co-primary outcomes for evaluating the effects of the 3 SMT protocol components on patient centered outcomes. The same analytic approach described above will be used. To account for 2 outcomes, we will again apply a 2-sided $\alpha=0.05$ and 97.5% CIs for statistical inference.

Secondary Aim #1: It is unknown how early SMT response may affect response to additional intervention. We will examine this question by evaluating responder status after 1 week as a possible effect moderator by adding a main effect for responder status and interaction terms between responder status and the indicator variables for treatments (and treatment combinations) which are retrained in the final simplified models for the different outcomes developed using the BIC criteria for each of the co-primary outcomes for the primary aims 1 and 2. Statistically significant interactions between responder status and main effect and/or interaction terms between treatment intervention components will be interpreted as suggesting effect moderation. Recognizing that tests for interactions have limited statistical power, we will also fit the simplified models developed in Aims 1 and 2 separately under the presence and absence of each factor (dichotomizing using a median split for continuous factors), and graphically display the estimated treatment effects at both levels of responder status. Recognizing the potential for lower statistical power, the results of Secondary Aim #1 will be interpreted as exploratory.

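### Interactions are part of both primary aims, but the power statement assigns limited power to secondary aims only; full-sample pairwise interactions on Oswestry and stiffness fall short of 80%, and no rule guards the word additive

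*Combined protocol and SAP*

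**What the plan says.** Section 1.1 puts interactions inside both primary aims. Aim I: "Identify SMT protocol components and interactions that independently predict SMT mechanistic outcomes (spinal stiffness and multifidus activation"). Aim II: "Identify SMT protocol components and interactions that independently predict SMT patient-centered outcomes (function, pain").

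Section 9.6 tests the three pairwise interactions and the 3-way interaction in all randomized participants for Primary Aim 1, and applies the same approach to Primary Aim 2. It gives this purpose: "Pairwise interactions will inform whether the effects of each intervention pair are additive, synergistic or antagonistic". For Aim 1 the tests use two-sided alpha 0.025 and "confidence intervals will be constructed using a confidence coefficient of 0.975". For Aim 2 the text reads "we will again apply a 2-sided $\alpha=0.05$ and 97.5% CIs for statistical inference", which is internally inconsistent.

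Section 9.2 claims 80% power or better for component main effects of the tabulated size on every outcome. It extends the claim to subgroup main effects and conditional comparisons, except for global stiffness. It then closes: "Power is more limited for secondary aims, such as pairwise interactions within subgroups". The prose says nothing about full-sample pairwise interactions. The table beside it has a row for them: 0.74 (stiffness), 0.064 (multifidus), 8.24 (Oswestry) and 1.53 (pain). There is no row for the 3-way interaction.

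**The concern.** A reader of the 9.2 prose would take it that everything under the primary aims is adequately powered and that only secondary questions are weak. For two of the four co-primary outcomes the table contradicts this, because the detectable interaction is larger than the effect the plan itself treats as important.

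The second half of the problem is interpretation. A significant interaction can support synergy or antagonism. Additivity is a claim of no material interaction, and at this power a non-significant test does not establish it. The plan does not say what result would count as additive. What is at stake is a primary-aim conclusion about how the components combine on Oswestry and stiffness.

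**Working it through.** **Inputs.** From section 9.2: analysed N = 280 × 0.92 = 257.6; SD 1.60 (stiffness), 0.124 (multifidus), 14.9 (Oswestry), 2.12 (pain); pre-post correlation 0.80, 0.70, 0.70, 0.45; MCID or hypothesized effect 0.40, 0.074, 6.0, 2.0. Alpha 0.025 two-sided is from 9.6 (Aim 1). Equal allocation to eight cells is from the Précis.

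**Formulas.** Residual SD = SD × √(1 − r²). SE(main effect) = 2 × residual SD / √N. SE(pairwise interaction, as a difference of differences) = 4 × residual SD / √N. Detectable effect at 80% power = (2.241 + 0.842) × SE = 3.083 × SE.

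**Reproducing the table.** √257.6 = 16.05.
- Stiffness: residual SD = 1.60 × √(1 − 0.64) = 0.960. Main effect 3.083 × 0.1196 = 0.369 (plan 0.37). Interaction 3.083 × 0.2393 = 0.738 (plan 0.74).
- Oswestry: residual SD = 14.9 × √(1 − 0.49) = 10.64. Main effect 3.083 × 1.326 = 4.09 (plan 4.12). Interaction 3.083 × 2.652 = 8.18 (plan 8.24).

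So these two columns rest on alpha 0.025, 80% power and N = 257.6. The table has no arithmetic error on this point. The SEs implied by the printed values are 8.24 / 3.083 = 2.673 and 0.74 / 3.083 = 0.240.

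**Power for an interaction of the tabulated MCID or hypothesized size**, Φ(effect/SE − 2.241), the opposite tail being negligible:

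| Outcome | SE from SD and r | Power | SE from table | Power |
|---|---|---|---|---|
| Oswestry, 6.0 | 2.652 | 50.8% | 2.673 | 50.1% |
| Stiffness, 0.40 | 0.2393 | 28.5% | 0.240 | 28.3% |
| Multifidus, 0.074 | 0.0221 | 86.7% | 0.0208 | 90.7% |
| Pain, 2.0 | 0.472 | 97.7% | 0.496 | 96.3% |

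With the 95% retention also quoted in 9.2 (N = 266), Oswestry is 52% and stiffness 29%. With alpha 0.05 for Aim 2 (critical value 1.960), Oswestry is 61% (table SE), 62% (SD and r) or 63% (N = 266). About 480 analysed participants (Oswestry) and 876 (stiffness) would be needed for 80% power at alpha 0.025.

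**Can additivity be shown?** If the true interaction is zero, the chance that the CI lies wholly within ±MCID is 2Φ((MCID − half-width)/SE) − 1, or zero if the half-width exceeds the MCID.
- Stiffness, 97.5% CI: half-width 2.241 × 0.240 = 0.54, above 0.40, so the chance is zero. With a 95% CI the half-width is 0.47, still above 0.40.
- Oswestry, 97.5% CI: half-width 5.94 (SD and r) or 5.99 (table), against 6.0. The chance is 1.7% or 0.3%, and 4.6% at N = 266.
- Oswestry, 95% CI: half-width 5.20 or 5.24. The chance is 24% or 22%, and 27% at N = 266.

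**3-way interaction.** Defined as a difference of pairwise interactions, its SE is twice the pairwise SE. The detectable effects are then 2 × 8.24 = 16.48 (Oswestry) and 2 × 0.74 = 1.48 (stiffness). The documents give no target for it, so no power is quoted.

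**The case against.** The shortfall is disclosed: the table prints 8.24 and 0.74 beneath 6.0 and 0.40, the 80% claim never extends to interactions, and the closing sentence of 9.2 gives subgroup interactions only as an example. This stands as far as it goes. The numbers are in the plan; the fault is that the prose points to secondary aims and passes over a primary one.

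A reader might infer that the plan will read every non-significant interaction as additive. No section says so. Section 9.6 promises estimates and CIs, with adjusted means for every combination. The gap is the lack of a criterion, not a stated wrong one.

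A reader might also infer that missed interactions lead to recommending components that work against each other. The documents do not support that. A missed interaction may be synergistic. An antagonistic one need not make a pair worse: two effects of 6 with an interaction of −6 give 6 + 6 − 6 = 6, the same as either alone. Conditional comparisons, which bear more directly on whether adding a component helps, reach 80% power for Oswestry (5.83 against 6.0). Optimized protocols are chosen under Secondary Aim 2 through BIC selection and simultaneous CIs, a route that an additive or inconclusive label does not alter.

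Finally, 9.2 says the correlations were set 4–7% below those observed. Undoing that for Oswestry (r = 0.70/0.96 to 0.70/0.93, about 0.73 to 0.75) raises power at alpha 0.025 to about 55–59% and the chance of showing additivity with a 97.5% CI to about 10–17%. Power stays below 80%.

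**Conclusion.** The point holds as a mismatch between the primary aims and the power narrative, together with a missing criterion for additivity. It concerns two of the four co-primary outcomes. At alpha 0.025, power for a pairwise interaction of the tabulated size is about 50% for Oswestry and 28% for stiffness; taking the printed 0.05 for Aim 2 moves Oswestry to about 61–63%. Multifidus and pain are adequate.

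Two assumptions carry these figures. The MCID or hypothesized effect is used as the interaction size, because the documents set none; a smaller target would lower power further. The alpha for Aim 2 is taken as 0.025, which the printed CIs and the Oswestry column support but the printed alpha does not.

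It would be tempting to say that additivity cannot be supported for either outcome. That is right for stiffness under the planning assumptions. For Oswestry it is too strong: the conclusion is unlikely (about 0.3–5% with a 97.5% CI, 22–27% with a 95% CI, if the true interaction is zero), but not impossible. The powered main effects are unaffected.

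**What to change.** In 9.2, state that full-sample pairwise interactions under the primary aims have less than 80% power at the MCID or hypothesized effect for Oswestry and global stiffness. Give the figures above with the alpha used, and say that taking the MCID as the interaction size is a choice. Note that the 3-way interaction is less precise still, with twice the standard error of a pairwise interaction when defined as a difference of pairwise interactions.

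In 9.6, state that a non-significant interaction will not be read as additive. Report the estimate and CI. Call a pair additive on an outcome only if the CI excludes an interaction of MCID (or hypothesized-effect) size in either direction; otherwise report it as inconclusive. Name the confidence level for this rule, and reconcile the alpha and CI level printed for Primary Aim 2. Add that, under the planning assumptions, the criterion cannot be met for stiffness and is unlikely to be met for Oswestry.

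The cost is protocol and SAP wording, a less favourable power statement and more inconclusive findings. No additional participants or procedures are needed.

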- Spinal Stiffness Measures: are obtained with a mechanically-assisted indentation device consisting of a motorized probe in an external frame. The probe contains a compressive-tension load cell. Displacement of the probe is measured by a linear variable differential transformer. Stiffness is assessed with the subject prone. The indentation probe is positioned over the L₃ spinous process. Indentation involves advancement of the probe from 5 N pre-load to 60 N final load maintained for 1 second. Three trials are performed with mean values used for analysis. Indentation data are used to calculate global stiffness (GS) (N) as the slope of the force displacement curve and terminal stiffness (TS) (N/mm) as the peak applied force and resultant displacement of underlying tissue.
- Lumbar Multifidus Activation Measures: are obtained with brightness-mode ultrasound images. The subject is prone with neck in neutral and arms overhead at about 120⁰ of shoulder abduction. Ultrasound transducer is placed just lateral to the spinal midline and angled medially until a parasagittal view of the multifidus at the L₄-L₅ and L₅-S₁ levels is obtained. Images are acquired at each level with the multifidus at rest and during submaximal contraction elicited by lifting the contralateral arm 2 inches while holding a weight proportional to body weight. Three images in each state are acquired and averaged. Muscle activation is calculated as change in thickness at rest and submaximal contraction.

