for analysis. Indentation data (force and displacement) are used to calculate stiffness variables. Global stiffness (GS) (N) is calculated as the slope of the force displacement curve between 5-60 N, representing stiffness of underlying tissues during indentation. Terminal stiffness (TS) (N/mm) represents peak applied force and resultant displacement of underlying tissues. We have found excellent within- and between-day reliability of stiffness measures made with this device (ICC = 0.98-0.99). A safety switch is provided to the subject and assessor that raises the indentation probe immediately if pressed, providing additional safety features.

Lumbar Multifidus Muscle Activation: Multifidus activation will be measured with brightness-mode ultrasound images using a 60mm, 2-5 MHz curvilinear array. We have previously reported excellent intra- and inter-rater reliability for these measures. The subject is prone with neck in neutral and arms overhead at about 120° of shoulder abduction. The ultrasound transducer is placed just lateral to the spinal midline and angled medially until a parasagittal view of the multifidus at the L₄-L₅ and L₅-S₁ levels is obtained. Images are acquired at each level with the multifidus at rest and during submaximal contraction elicited by the subject lifting the contralateral arm about 2 inches while holding a weight proportional to body weight. Images are acquired at the end of exhalation to minimize effects of respiration. Three images in each state are acquired and averaged. Images are stored and measured offline by a blinded rater using NIH (Bethesda, MD) Image J software (V1.38t). Offline multifidus thickness measures are obtained from determining the distance between the posterior-most aspect of the facet joint inferiorly and the plane between the multifidus and thoracolumbar fascia superior. Activation is calculated as the change in thickness from rest to submaximal contraction ($\text{Thickness}_{\text{contract}} - \text{Thickness}_{\text{rest}}$) / $\text{Thickness}_{\text{rest}}$). Research has shown these measures of multifidus activation have good concurrent validity compared to EMG activity of the muscle.

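### Power table in section 9.2: the multifidus main effect and the four entries below it cannot come from one calculation, and the mm heading does not fit the unitless ratio defined for analysis

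*Combined protocol and SAP*

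**What the plan says.** Section 9.2 sets the basis of the table: "Assuming a sample size of 316, of which 280 meet all eligibility criteria and 92% of enrolled participants are retained to 4 weeks". It lists detectable effects for main effects, pairwise interactions, a conditional comparison ("comparison of mean outcome between two levels of one component at a fixed level of another component"), and main effects and interactions in half the participants. It claims at least 80% power for main effects on all outcomes, and for half-sample main effects and conditional comparisons on all outcomes except global stiffness. It says that power is more limited for pairwise interactions within subgroups.

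The multifidus column, with a heading that begins "Multifidus Activation (mm", gives mean (SD) 2.60 (0.124), pre-post correlation 0.70, target 0.074, and detectable effects 0.034, 0.064, 0.045, 0.045 and 0.091.

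Section 9.6 gives the outcome its standing: "Spine stiffness and multifidus activation will be co-primary outcomes for evaluating effects of SMT protocol components on SMT mechanisms". On significance levels it says "To account for 2 primary outcomes, each of the hypothesis tests noted above will be performed with 2-sided" alpha of 0.025.

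The outcome is described twice. Section 6.2.2.2: "Muscle activation is calculated as change in thickness at rest and submaximal contraction". Section 9.5.1: "Activation is calculated as the change in thickness from rest to submaximal contraction", followed by a formula that divides the change by the resting thickness.

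**The concern.** The five detectable effects in a column differ only by multipliers that the design fixes, so one column can be checked against itself without knowing the SD, alpha or sample size. The multifidus column fails that check and the other three pass. At least one of its printed figures is therefore wrong.

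The unit is a second, separate matter. A thickness change in mm and a change divided by resting thickness are different variables. This table is the only sample-size justification, and multifidus activation is co-primary for Aim 1. Until the scale is stated, a reader cannot tie the SD and the 0.074 target to the variable that will be analysed.

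**Working it through.** **Multipliers.** With equal allocation to the eight combinations, each component splits the sample in half, and a main effect has standard error 2s/√N, where s is the residual SD. A conditional comparison uses half the sample: √2 times as large. A pairwise interaction is the difference between two independent conditional comparisons: 2 times. Halving the sample multiplies each by √2, so the half-sample main effect is 1.41 times and the half-sample interaction 2.83 times the main effect.

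**Check within each column.** Ratio of each printed entry to the printed main effect, and the range of main effects from which all the entries could round:

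| Column | Interaction | Conditional and half-sample main | Half-sample interaction | Common main effect |
|---|---|---|---|---|
| Expected | 2 | 1.41 | 2.83 | |
| Stiffness | 2.00 | 1.43 | 2.84 | 0.371-0.3725 |
| Oswestry | 2.00 | 1.42 | 2.83 | 4.119-4.121 |
| Pain | 2.01 | 1.42 | 2.84 | 0.7625-0.765 |
| Multifidus | 1.88 | 1.32 | 2.68 | none |

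For multifidus, the printed 0.034 allows 0.0335-0.0345. The four lower entries agree with each other only at 0.0320-0.0322. The two ranges do not overlap. Put the other way, 0.0335-0.0345 allows 0.067-0.069, 0.047-0.049 and 0.095-0.098 in the lower rows; 0.064, 0.045 and 0.091 all fall outside.

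**Which part fits the stated inputs.** N = 0.92 × 280 = 257.6; SD 0.124; r = 0.70; two-sided alpha 0.025; power 80%; baseline adjustment as in ANCOVA (section 9.6).

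Detectable main effect = (2.241 + 0.842) × SD × √(1 − r²) × 2/√N = 3.083 × 0.124 × 0.714 × 2/16.05 = 0.0340.

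This reproduces the printed main effect. The multipliers then give 0.0680, 0.0481, 0.0481 and 0.0962. With t quantiles at N of 256 to 258, the main effect is 0.0342-0.0343 and the lower rows are 0.068-0.069, 0.048-0.049 (twice) and 0.097.

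**Cross-check from the table alone.** Oswestry has the same correlation, 0.70. With a common N, alpha and method, multifidus must equal Oswestry × 0.124/14.9. From 4.12 this gives 0.0343, 0.0686, 0.0485, 0.0485 and 0.0970, which again agrees with 0.034 and not with the lower four.

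**N implied by the printed multifidus entries** (same formula): 258 for the main effect; 291, 294, 294 and 288 for the rows below.

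**Power for the 0.074 target** = Φ(0.074 × 3.083/entry − 2.241):
- Pairwise interaction: 87% at 0.0680 and 86% at 0.0686; the printed 0.064 implies 91%.
- Half-sample interaction: 55% at 0.0962 and 54% at 0.0970; the printed 0.091 implies 60%.
- Main, conditional and half-sample main effects: above 99% with printed or recomputed entries.

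No entry crosses 0.074 on recomputation.

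**Unit.** The table heading is in mm; the section 9.5.1 formula has no unit; section 6.2.2.2 gives no divisor. Detectable effects depend on the SD and the correlation, not on the mean, and the target is 0.074/0.124 = 0.60 SD. If SD, correlation and target are all on the analysed scale, the heading does not affect power.

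**The case against.** The strongest objection is that exact replacement values are not established. The normal formula at N = 257.6 does not fully reproduce any other column. It gives Oswestry 4.09 against 4.12 and pain 0.73 against 0.76, with every row of both columns missed, and in the stiffness column it gives 0.52, 0.52 and 1.04 where 0.53, 0.53 and 1.05 are printed. The sponsor's method evidently differs in some detail. This stands, and it is why the replacements are given as ranges. It does not touch the ratio check, which uses no formula for N or alpha. The Oswestry cross-check needs only a method common to the two columns. It does assume a common alpha: section 9.6 gives 0.05 together with 97.5% intervals for Aim 2, but the printed 4.12 lies close to the 0.025 result (4.09) and not the 0.05 result (3.71).

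A reader might infer three stronger things that the documents do not support:
- **A known source of the error.** Taking 92% of 316 (290.7) gives 0.0320, 0.0640, 0.0453, 0.0453 and 0.0906, which matches all four lower entries. But a change-score variance at N = 280 and alpha 0.05 also comes close, and neither gives 0.034.
- **A mean and SD on different scales.** As a ratio, 2.60 would mean a contracted thickness 3.6 times the resting one, and SD/mean is 4.8% against 29%-61% in the other columns. This raises the question but proves nothing, since unlike instruments need not share a coefficient of variation.
- **Conflicting outcome definitions.** Section 6.2.2.2 is a shorter description in nearly the same terms as section 9.5.1. It is incomplete and is not shown to contradict the formula. The conflict is between the table heading and section 9.5.1.

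**Conclusion.** The multifidus column is inconsistent as printed; this is certain from the ratios alone. The stated inputs and the Oswestry column both side with 0.034, so the four lower entries are about 5%-7% too favourable. The conflict between the mm heading and the unitless ratio is also real.

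Both are minor. A reader might infer that the trial is underpowered for multifidus activation, but the documents do not support that. The 80% statement for main, half-sample main and conditional effects holds with room to spare, the pairwise interaction keeps about 86%-87% power, and the half-sample interaction was short of 80% on the printed figure too. These power figures assume that the SD, correlation and 0.074 are on the section 9.5.1 scale. The documents neither show this nor contradict it beyond the heading.

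**What to change.** Recompute the whole multifidus column with the method used for the other columns. Expected values are about 0.034, 0.068-0.069, 0.048-0.049, 0.048-0.049 and 0.096-0.097; the sponsor's own calculation should supply the final digits. If the four lower entries are kept instead, the main effect must read 0.032, and the N of about 291 behind the column must be reconciled with 92% of 280.

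State the unit in the table (none, if a ratio). Confirm that the mean, SD, correlation and 0.074 target are on the section 9.5.1 scale, or restate them on it. Add the divisor to section 6.2.2.2 so that it matches section 9.5.1.

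The cost is text and table edits only, with no extra participants, visits or analyses.
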